## **6.1. Power Analysis**

We are working with our data management group to develop the 90-day total cost of care measure. With this version of the protocol we can only estimate cost savings. In the literature, studies on behavioral health integration tend to evaluate symptom improvement or utilization. Blue Cross Blue Shield of Kansas City data were used to conduct a case control program evaluation in 2018. This study assessed the cost effectiveness of embedding a Behavioral Health Clinician into an Existing Primary Care Practice. Though not virtual, we would assume a similar direction in cost saving reduction in our program. The results demonstrated that integrating behavioral health services into the practice was associated with \$860.16 per member per year savings or 10.8% savings in costs.

## **6.2. Statistical analysis**

Prior to analysis, descriptive statistics will be calculated to screen all variables for accuracy and to examine distributions.

All analyses will follow the intention-to-treat (“ITT”) principle, such that patients will be analyzed based on the assignment of their primary care site to the VBHI program or usual care. Balance in baseline characteristics between the groups will be assessed using Student’s t-test for normally distributed data, the Wilcoxon rank sum test for ordinal data or interval data that are not normally distributed, and the chi-square test for categorical data. Normality will be assessed using the Shapiro Wilk test and Q-Q plots.

The primary outcome, total cost of care, will be compared between the VBHI and usual care groups using a linear mixed-effects model with a random effect to account for within-practice correlation. The primary predictor in the model is an indicator for assignment to the VBHI program versus usual care. Additional baseline covariates will be included in the model if they are either strongly correlated with the dependent variable or show baseline imbalance between the two groups.

The secondary outcome of pharmacy-related total cost of care will be compared between treatment groups using the same approach as for the primary outcome. A similar approach will be used to compare 90-day patient-centric, primary care, and avoidable care utilization rates, except the models will be generalized linear mixed models with a logit link, where utilization (yes/no) is the binary dependent variable.

Sub-analyses of the primary and secondary outcomes using the above methods will be performed on the data stratified by index primary care visit diagnosis.

In addition, per-protocol analyses of the primary and secondary outcomes will be performed to evaluate the effect of VBHI program participation, in contrast to the ITT analysis evaluating the effectiveness of referral to the program. The per-protocol analyses will include only subjects who received and adhered to the treatment (VBHI program or usual care) assigned to their clinic. The analyses will be similar to those described above for ITT, except the primary predictor is an indicator for treatment (VBHI program or usual care) received rather than treatment assigned. To help address confounding due to incomplete adherence, the per-protocol analyses will adjust for pre-randomization and post-randomization factors that predict adherence. To identify such factors, a separate, multivariable logistic regression analysis will be performed on the full dataset with adherence (yes/no) as the dependent variable.

Exploratory analyses will evaluate baseline to 3-, 6-, 9-, and 12-month changes in symptom improvement and health outcomes using generalized linear mixed models with a logit link, where the dependent variable is binary (e.g., 50% reduction of PHQ-9 score from initial assessment (yes/no)). Random effect terms in the model will account for within-practice clustering and within-patient correlation. Fixed effects will be the treatment group indicator, time indicator, and interaction between treatment group and time.

All tests will be two-sided and the data will be analyzed using SAS Enterprise Guide 7.1 (SAS Institute Inc., Cary, NC, USA).

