Statistical Analysis	Analyses will include all patients meeting the inclusion and exclusion criteria. Comparisons of the intervention and usual care groups will be made using univariate analyses such as the t-test and chi-square test. The primary outcome, the 90-day total cost of care, will be compared between the two groups of patients using a generalized linear mixed model. Results will be presented with odds ratios and 95% confidence intervals.
-----------------------------	--

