### **1.3. Secondary Objectives**

For the primary and secondary objectives, patients will be followed up to 90 days.

- Compare demographics, Charlson comorbidity index, and social determinants of health among patients (hunger vital signs, home, education, employment, social and emotional health) between the two arms of the study
- Compare the patient-centric 90-day utilization rate after the index primary care visit
- Compare the 90-day primary care utilization rate after the index primary care visit
- Compare the pharmacy related 90-day total cost of care after the index primary care visit
- Stratify and report outcomes by index primary care visit diagnoses (substance use disorder, depression/dysthymia, anxiety)

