## **4. SUBJECT AND SITE SELECTION**

### **4.1. Accrual – Primary Care Practices**

Randomization will occur at the practice level with the primary care practices being identified as an intervention or usual care site for the duration of the study. Out of 20 primary care clinics that have shown interest in the VBHI program, 10 will be randomized into the intervention arm and 10 into the usual care arm. Not all sites in the intervention arm are starting the program immediately. There will be a scheduled rollout of 2-3 clinics per month. As intervention sites come on board, a corresponding control site will begin contributing to the evaluable population. Twelve practices indicated their readiness to incorporate the VBHI program into patient care in 2019 with the remaining indicating 2020. A practice labeled as low volume had historically averaged 15 or less eligible patients per month. A practice labeled as high volume had historically averaged 16 or more eligible patients per month.

Twelve practices were identified by the behavioral health team for a 2019 rollout based on the readiness to engage with the VBHI program in 2019. Practices were clustered by patient volume per month (low n=8, high n=4). The 8 practices with lower volumes were randomly ordered and assigned as either a case or control (1:1). The 4 practices with higher volumes were randomly ordered and assigned as either a case or control (1:1). The six primary care practices and corresponding matched control practice were then randomly ordered for a 2019 rollout. Each month that a practice starts using the VBHI program, patients start accruing from the randomly matched control practice.

Eight practices were identified by the behavioral health team for a 2020 rollout based on the readiness to engage with the VBHI program in 2020. These practices were not ready to engage in 2019. Practices were clustered by patient volume per month (low n=4, high n=4). The 4 practices with lower volumes were randomly ordered and assigned as either a case or control (1:1). The 4 practices with higher volumes were randomly ordered and assigned as either a case or control (1:1). The four primary care practices and corresponding matched control practice were then randomly ordered for a 2020 rollout. Each month that a practice starts using the VBHI program, patients start accruing from the randomly matched control practice.

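### The between-arm comparison of baseline characteristics, a listed secondary objective, uses patient-level tests although practices are randomised

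*Combined protocol and SAP*

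**What the plan says.** Section 4.1: "Randomization will occur at the practice level", and of 20 practices "10 will be randomized into the intervention arm and 10 into the usual care arm". Allocation was 1:1 within four groups formed by rollout year and patient volume: 8 low-volume and 4 high-volume practices for 2019, and 4 and 4 for 2020.

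Section 1.3 lists as its first secondary objective: "Compare demographics, Charlson comorbidity index, and social determinants of health among patients", between the two arms.

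Section 6.2 assesses balance with three tests. Student's t-test is for variables that look normal; the other two are "the Wilcoxon rank sum test for ordinal data or interval data that are not normally distributed, and the chi-square test for categorical data". It describes no adjustment for practice here. The same section gives the cost model a random effect for practice, takes the same or a similar approach for the other outcomes, and includes a practice term in the exploratory models.

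Covariates enter the cost model if they are strongly correlated with cost "or show baseline imbalance between the two groups".

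The Statistical Analysis entry of the Protocol Summary says: "Comparisons of the intervention and usual care groups will be made using univariate analyses such as the t-test and chi-square test". It does not restrict that sentence to baseline.

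**The concern.** Age, race, insurance plan, comorbidity and social circumstances can be expected to differ between practices. With ten practices per arm, chance alone will leave the arms somewhat different on such variables. A test that counts patients as the independent units underestimates that chance variation, so its p-value is too small.

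Two things are at stake. First, a declared secondary objective has no other method in the plan, and the one it has does not hold its error rate. A small p-value could not be read as evidence that different kinds of patients entered the two arms. Second, the covariate rule in section 6.2 does not define imbalance. If these p-values are used to define it, they influence which covariates enter the primary cost model after the data have been seen.

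**Working it through.** **No figure to reproduce.** The plan states no sample size, power, ICC or significance level. The check therefore rests on the design in section 4.1 and on stated assumptions.

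**Inputs from the documents.** 20 practices, 10 per arm, in groups of 8, 4, 4 and 4; low volume means at most 15 eligible patients a month and high volume at least 16 (section 4.1); accrual of 17 months with staggered starts (section 4.2); two-sided tests (section 6.2).

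**Assumptions.** A 5% level, suggested only by the 95% intervals in the Protocol Summary. ICC 0.005 to 0.10, with 0.001 as a sensitivity value. Patients per practice m from 50 to 340: 5 a month × 17 = 85 and 20 a month × 17 = 340, with 50 allowing for smaller or later-starting practices. The ICC here is the similarity within a practice that the stratification does not explain.

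**Formulas.** Design effect DE = 1 + (m − 1) × ICC. Actual two-sided rate = 2 × [1 − Φ(1.96 / √DE)].

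- m = 50, ICC 0.005: DE = 1 + 49 × 0.005 = 1.245; rate 7.9%.
- m = 85, ICC 0.005: DE = 1 + 84 × 0.005 = 1.42; rate 10.0%.
- m = 340, ICC 0.05: DE = 1 + 339 × 0.05 = 17.95; rate 64.4%.
- m = 340, ICC 0.10: DE = 1 + 339 × 0.10 = 34.9; rate 74.0%.

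False-positive rate of a nominal 5% test:

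| Patients per practice | ICC 0.001 | 0.005 | 0.01 | 0.02 | 0.05 | 0.10 |
|---|---|---|---|---|---|---|
| 50 | 5.6% | 7.9% | 10.8% | 16.4% | 29.1% | 42.0% |
| 85 | 6.0% | 10.0% | 14.8% | 23.1% | 39.0% | 52.3% |
| 170 | 7.0% | 14.9% | 23.2% | 34.9% | 52.4% | 64.3% |
| 340 | 9.0% | 23.3% | 35.0% | 48.2% | 64.4% | 74.0% |

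**Simulation.** The formula assumes equal practice sizes. A simulation used unequal ones: 20 practices randomised within the 8/4/4/4 groups, assumed volumes of 5 to 15 a month (low) and 16 to 25 (high), 9 to 17 months of accrual, averages of 116 to 323 patients per practice, no arm effect, and 4,000 runs per setting. The patient-level t-test and chi-square test gave similar results: 22–35% at ICC 0.01, 33–48% at 0.02, 51–65% at 0.05 and 63–74% at 0.10. With ICC essentially zero the t-test rejected in 4.6–5.2% of runs, so clustering is the cause of the excess.

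**Remedy checked.** A t-test on practice means (10 against 10, 18 df) rejected in 4.9%, 5.0% and 5.1% of simulated trials at ICC 0.01, 0.05 and 0.10.

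**The case against.** The strongest reply is that this is a baseline comparison and the outcome inference is sound on this point. That largely stands. The cost, pharmacy and utilisation models account for practice, and no bias or loss of power has been shown for any of them. A reader might infer that the primary result is invalid; the documents do not support that. The only route to it is the covariate rule, which section 6.2 neither defines by a p-value nor ties explicitly to these tests, although that is a natural reading.

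Other stronger readings also fail:

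- A reader might take one inflation figure as a property of this trial. The documents fix none of the inputs that determine it.
- A reader might call the imbalances themselves false. A difference in age or comorbidity left by randomising practices is real in the sample and may merit adjustment. What is wrong is the p-value as evidence against chance allocation.
- A reader might add that confidence intervals will be too narrow. Section 6.2 plans none for baseline characteristics.
- A reader might see these tests as the sole safeguard against selective entry after unblinded allocation. The documents do not discuss blinding. They describe PHQ screening for all patients in both arms, and section 4.4 assesses everyone who meets the criteria.
- A reader might take the Summary sentence to mean unclustered tests of outcomes. It is loose wording, followed at once by the mixed model for cost, and section 6.2 confines these tests to baseline balance.

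None of this removes the defect. The comparison is a listed objective, and the tests named for it do not match the unit of randomisation.

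**Conclusion.** The analysis of the first secondary objective is wrong as written. That follows from sections 4.1 and 6.2 without any assumption about size: the false-positive rate exceeds nominal for any ICC above 0 remaining within the randomisation groups. Its size is conditional. With an assumed 5% level, ICC 0.005 to 0.10 and roughly 50 to 340 patients per practice, it is about 8% to 74%; at ICC 0.001 it would be only 5.6% to 9.0%. The wording should be corrected before analysis, but this does not by itself put the primary comparison in doubt.

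**What to change.** In section 6.2 and the Protocol Summary, replace the unclustered tests with descriptive summaries by arm and standardised differences.

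Where inference is wanted for the secondary objective, treat practice as the unit of randomisation:

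- compare practice means or proportions, 10 against 10 with 18 df, or fit a mixed model with a practice random effect and small-sample degrees of freedom;
- for multi-category variables such as race, insurance plan, housing and education, use category proportions by practice or a multinomial or ordinal model;
- for skewed variables, use practice-level medians or ranks.

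Do not select covariates by these p-values; name the cost model's covariates in advance.

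One point needs confirming alongside. Section 5.1.2 records the social variables at enrolment. If that means enrolment in the VBHI programme, usual-care values may not exist, and no choice of test would supply them.

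The cost is revised wording and a little more code, with no new data, sites or patients. Fewer baseline differences will be called significant.

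### The four wave-by-volume randomisation strata are not prespecified in the primary cost model; a covariate rule with no threshold decides whether they enter

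*Combined protocol and SAP*

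**What the plan says.** Section 4.1 splits the practices by readiness (2019 or 2020 rollout) and by historical volume: "A practice labeled as low volume had historically averaged 15 or less eligible patients per month", and high volume means 16 or more. Assignment is 1:1 separately within each of the four resulting groups.

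Section 6.2 compares total cost of care "using a linear mixed-effects model with a random effect to account for within-practice correlation". It then states: "The primary predictor in the model is an indicator for assignment to the VBHI program versus usual care". The only route for any other term is: "Additional baseline covariates will be included in the model if they are either strongly correlated with the dependent variable or show baseline imbalance" between the groups. Balance is to be checked with a t-test, a Wilcoxon test, "and the chi-square test for categorical data". No correlation cut-off, p-value or standardised difference is given.

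Wave and volume do not appear among the variables listed in 5.1.2, and no section says that the strata will be in the primary model. Section 6.2 also names no degrees-of-freedom method for the mixed model.

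**The concern.** When randomisation is stratified, the strata are balanced by design. If they also predict the outcome, a model that omits them counts between-stratum variation as noise that the design has already removed from the arm contrast. The model-based standard error is then too large, the test is conservative, and a real saving is more likely to be missed. With only 20 practices and no stated power, there is no evident margin to give away.

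The rule in 6.2 does not settle whether the strata enter. It can be read in at least three ways:

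- **A.** Wave and volume are never screened, because they are not listed characteristics.
- **B.** The four-level stratum is screened at patient level by chi-square and added if p<0.05.
- **C.** Wave and volume are screened at patient level as two separate characteristics, each added on its own result.

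Under B or C the content of the primary model is decided after the data are seen. The trigger is how far practice sizes happen to differ between arms within a stratum, which says nothing about whether the stratum predicts cost.

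**Working it through.** **Inputs from the documents.** Strata of 8, 4, 4 and 4 practices (4.1): 8+4+4+4 = 20 in total and 4+2+2+2 = 10 per arm, as stated. Tests are two-sided (6.2). The documents give no sample size, power, alpha, SD or ICC, so there is no planned figure to reproduce. Alpha 0.05 is assumed from the 95% intervals in the protocol summary.

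**Would the rule admit the strata?**

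- *Imbalance, counting practices:* the strata are exactly balanced, so no.
- *Imbalance, counting patients:* this depends on the coefficient of variation (CV) of practice size within a stratum. Reading B adds the strata in about 5% of simulated trials at CV 0, 40–54% at CV 0.1, 78–87% at CV 0.2 and 91–95% at CV 0.3. At CV 0.2, reading C adds both terms in 25–33% of trials and neither in 19–25%.
- *Strong correlation with cost:* the patient-level correlation is √(share × ICC), where share is the proportion of between-practice variance that the strata explain. For assumed shares of 25–50% and ICC 0.01–0.05, this runs from √(0.25×0.01) = 0.05 to √(0.50×0.05) = 0.16. Few analysts would call that strong.

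**What follows if they are left out?** Simulation, 6,000 trials per setting, all inputs assumed:

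- Randomisation within 8/4/4/4; low-volume practices average 8 and high-volume 24 eligible patients per month; practice-size CV 0.2.
- Accrual of 17 months at every practice, or 15 and 9 months by wave.
- ICC 0.01 and 0.05; stratum effects drawn at random.
- Practice-level REML with a t reference on 18 df less the terms added.

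Each entry is type I error, then power at an effect giving 80% with strata prespecified. Ranges span both ICCs and both accrual patterns. Monte Carlo SE is about 0.3 points at 5% and 0.5 points at 80%.

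| Share | A (never in) | B | C |
|---|---|---|---|
| 0% | no loss | no loss | no loss |
| 10% | 3.8–4.6%; 78–79% | 4.6–5.3%; 80% | 4.3–4.8%; 78–79% |
| 25% | 2.4–3.8%; 71–75% | 4.4–5.2%; 78–79% | 3.3–4.4%; 74–77% |
| 50% (extreme) | 0.8–1.8%; 53–66% | 4.0–5.1%; 75–78% | 1.9–3.0%; 63–71% |

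With the strata always in, type I error is 4.6–5.6% at every share. Under A the SE is 9–16% too large at a 25% share and 22–40% at 50%. At CV 0.1 and a 25% share, power is 75–77% under B and 73–76% under C. Skewed patient costs (gamma, CV 3) give the same pattern: at a 25% share, type I error is 2.4–3.6% under A and 4.5–5.1% under B.

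**Cross-check on practice means.** A simpler simulation (20,000 trials per setting) compared an arm-only t test on 18 df with arm plus strata on 15 df. The stratum effect was placed on volume, and the share was of the variance of practice means. For shares of 0, 20, 40 and 60%, omitting the strata gave type I error of 5.0, 2.8, 1.2 and 0.2% and power of 81, 73, 60 and 35%. With strata these stayed at 4.9–5.2% and about 80%.

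**Degrees of freedom.** Residual df are 20−2 = 18 without strata and 20−4−1 = 15 with them. Critical values are 2.101 and 2.131, a ratio of 1.015. If 1.96 is used instead, P(|t₁₈|>1.96) = 6.6% and P(|t₁₅|>1.96) = 6.9%. In the main simulation a normal reference with strata rejects 6.4–7.6% under the null. Without strata it rejects 6.0–7.3% at a 0% share, 5.4–6.2% at 10% and 3.5–5.1% at 25%.

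**The case against.** The strongest reply is that the documents show no harm. Nothing in them links volume or readiness wave to cost per patient, every loss figure rests on an assumed share, and at 10% the loss is at most about two points of power. That stands, and it is why the point is minor.

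Second, wave and volume are practice-level factors, so the correlation could be judged on practice means. Shares of 25–50% then correspond to √0.25 = 0.50 to √0.50 = 0.71, or about 0.38–0.69 after sampling noise, and the strata might well be admitted. This is a possible reading, but the dependent variable in 6.2 is patient-level cost. Even at practice level, a cut-off of 0.5 (the plan gives none) was exceeded in only 43–77% of simulated trials at those shares.

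Third, the p<0.05 in reading B is supplied here, and 6.2 does not confine covariates to the 5.1.2 list. Both are true, and both illustrate how open the rule is.

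Fourth, the SE figures are averages. In a smaller run (1,500 trials per setting, 17-month accrual) the median widening of the interval under A was about 4–7% at a 25% share and 13–21% at 50%, against mean widening of 9–14% and 22–38% in the main simulation. The typical trial loses less than the mean suggests.

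Fifth, the benefit depends on a small-sample reference distribution, a separate omission. That is correct, and the fix therefore pairs the two.

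Finally, 4.1 also describes matched controls and staggered starts. Pair and start-month terms were not evaluated. Ten pair intercepts would leave 20−10−1 = 9 df, a different trade-off.

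**Conclusion.** The concern holds as a minor, inexpensive improvement. The text is clear: the design strata are not in the primary model, and the only way in is a rule that neither names them nor sets a threshold. No bias is shown, and no inflation of type I error from omitting the strata under a t reference. The loss is conditional on strata that predict cost. At a 25% share it is 5–9 points of power if they are never entered (80% down to 71–75%), 3–6 points under reading C and 1–2 points under reading B. At a 0% share there is none. These sizes rest on the assumed practice volumes, size variation, ICC and share, none of which the documents give. Independently of size, under readings B and C the primary model is settled after seeing the data by a check unrelated to prognosis, which prespecification would avoid.

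**What to change.** In 6.2, state that the linear intention-to-treat models for total cost and pharmacy cost include the four wave-by-volume strata as a fixed factor, whatever the covariate screen shows. In the same sentence, name a small-sample method for the arm test and confidence interval, for example Kenward-Roger (about 20−4−1 = 15 df). The two belong together, since strata with a normal reference over-reject.

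The protocol summary describes the primary cost analysis as a generalized linear mixed model reported with odds ratios. That conflict with 6.2 needs its own resolution. The strata term carries over to whichever model is kept, but the figures here apply to the linear one. Adding strata to the logit utilisation models is optional, and its gain was not quantified.

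The cost is one SAP sentence and one model statement, and every practice's stratum is already known. If the strata do not predict cost, the price is 3 df, an interval about 1% wider and about one point of power (81% to 80%). Type I error in that case is 4.9–5.6% with strata and 4.9–5.4% without (20,000 trials per setting).

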### **4.2. Accrual – Subjects**

Patients 18 years of age or older at primary care practices with a PHQ-9 overall score  $>10$  or Question 9  $>0$ , and with Medicare or other value-based contract where the VBHI program is offered will be considered exposed to the intervention; whereas, patients seen at sites not utilizing the VBHI program will be considered exposed to usual care. Patients who are in the intervention arm will be treated by the behavioral health care team (licensed clinicians, health coaches, a psychiatric pharmacist and psychiatric providers). Virtual visits are conducted either by video assessment or telephonically. As part of the current care process, all patients with a primary care visit are given the PHQ-2 survey. A score  $\geq 2$  triggers the PHQ-9 survey. Patients who present to participating primary care practices with an elevated patient health questionnaire (PHQ-9) score or report suicide ideation (Question 9) will be

treated and followed per the proposed virtual behavioral health integration (VBHI) program or usual care. Each weekday a list of patients is received by the behavioral health care team. The list includes patients with an elevated PHQ-9 score from the prior day and the associated insurance plan for the patient. The insurance plan is included so that the behavioral health team can target patients with Medicare

or other value-based contracts that report total costs back to Atrium Health. On Mondays, the team receives a list of patients seen between Friday and Sunday.

Patients included in the analysis of this study must meet the inclusion\exclusion criteria and have an insurance claim for the index primary care visit when they became eligible in the enterprise data warehouse (EDW). Patients will begin accruing based on the time the practice goes live according to the role out schedule and will continue for 17 months. The VBHI program is available to any patients in the practice but the evaluation is centered on the cohort of patients meeting the inclusion criteria.

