### 6. DATA COLLECTION AND REPORTING

Patient demographics, Charlson comorbidity score, and utilization will be obtained from the electronic medical record and billing systems. Data from the initial assessment and follow-up contacts will be stored in HealtheCare, a care management platform in Cerner. Data will be retrieved by an application specialist on the research team. Data may be retrieved retrospective to a patient’s completion of the intervention or usual care arm of the study. A participation rate can be generated from the count of patients enrolled in the VBHI program over the count of patients meeting the inclusion criteria.

A bi-monthly report will be produced for the intervention arm. The report will be by primary care practice and overall showing the prior 2 weeks of activity.

- Count of patients meeting the inclusion criteria
- Count of patients with a HealtheCare account
- Count of patients enrolled in the VBHI program
- Patient list with their enrollment status in HealtheCare

A monthly report will be produced for the intervention arm. The report will be by primary care practice and overall. Report to be generated 2 weeks after the end of the month showing the prior month of activity.

- Count of patients meeting the inclusion criteria
- Count of patients with a HealtheCare account
- Count of patients enrolled in the VBHI program
- Patient list with their enrollment status in HealtheCare

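### The primary cost model chooses its covariates from the data by undefined triggers and gives no assured place to volume group and rollout year, the factors within which practices were randomised

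*Combined protocol and SAP*

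**What the plan says.** Protocol section 6.2 compares 90-day total cost with a linear mixed-effects model. It contains an indicator for assignment and a random effect for practice. For everything else the rule is that "covariates will be included in the model if they are either strongly correlated with the dependent variable or show baseline imbalance" between the two groups. No correlation cut-off, imbalance cut-off or list of candidates is given there or elsewhere. The variables in section 5.1.2 are listed for description and comparison, not as model terms.

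The same section assesses baseline balance by Student's t-test, "the Wilcoxon rank sum test for ordinal data or interval data that are not normally distributed, and the chi-square test for categorical data". It attaches no threshold to these tests and makes no allowance for clustering.

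The rule reaches beyond the primary outcome. Pharmacy cost "will be compared between treatment groups using the same approach as for the primary outcome", the utilization models follow a similar approach, and "Sub-analyses of the primary and secondary outcomes using the above methods will be performed" by index-visit diagnosis.

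On design, section 4.1 states: "Randomization will occur at the practice level". For the 2019 rollout, "Practices were clustered by patient volume per month (low n=8, high n=4"); for 2020 the split is 4 and 4. Practices were assigned 1:1 within each of these four cells, and each intervention practice was paired with a control that starts accruing in the same month. Neither section 6.2 nor the Protocol Summary puts volume group, rollout year, pair or go-live month into the model.

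**The concern.** Two analysts who follow section 6.2 faithfully can fit different primary models to the same data. One of the two triggers needs the cost data, so the model cannot be settled before outcomes are available.

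The imbalance trigger has a further weakness. On the natural reading, which the text does not state outright, imbalance is judged by the patient-level tests named in the same section. Practices were randomised, not patients, so those tests understate the chance variation between arms and flag too many differences.

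The randomisation factors are in an odd position. They are balanced by practice count by design, so they can enter only through uneven patient numbers or through an undefined strong correlation with cost. If they stay out and are related to cost, their variation remains in the between-practice error although randomisation has removed it from the arm contrast. The standard error is then too large. At stake are precision in a trial of 20 practices and the credibility of a primary result whose model was not fixed.

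**Working it through.** **Inputs from the documents.** 20 practices, 10 per arm; randomisation cells of 8, 4, 4 and 4 (8+4+4+4 = 20; 4+2+2+2 = 10 per arm, which agrees with section 4.1). Tests are two-sided (section 6.2). The 0.05 level is inferred from the 95% intervals in the Protocol Summary. There is no SD, ICC, planned total or power figure to reproduce.

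On numbers, the documents give only volume cut-offs (15 or less, 16 or more eligible patients per month) and 17 months of accrual. A high-volume practice at the cut-off and live throughout would have 16 × 17 = 272 eligible patients, before repeat visits and missing claims; later starters have fewer.

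**Assumed.** ICC 0.01-0.05, 50-100 patients per practice unless stated, and a normal outcome.

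**1. False flags from patient-level balance tests.** With m patients per practice, the true flag rate of a nominal 5% test is 2 × P(Z > 1.96/√(1+(m−1)·ICC)).

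| m | ICC 0.01 | ICC 0.02 | ICC 0.05 |
|---|---|---|---|
| 50 | 10.8% | 16.4% | 29.1% |
| 100 | 16.5% | 25.6% | 42.2% |

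For example, m = 50 and ICC 0.01 give a design effect of 1.49. At m = 150 the range is 21.4% (ICC 0.01) to 50.0% (ICC 0.05), so larger practices make this worse.

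**2. Leaving out volume and year.** Twelve of 20 practices are low-volume and 12 of 20 are 2019 practices, so each factor has variance 0.4 × 0.6 = 0.24. Four of 20 are both high-volume and 2020, so the covariance is 0.20 − 0.16 = 0.04. A shift of s SD in the same direction on each adds (0.24 + 0.24 + 2 × 0.04)s² = 0.56s² to the variance between practice means: 0.0014, 0.0056 and 0.0126 for s = 0.05, 0.10 and 0.15.

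The 1:1 cells balance this out of the arm difference but not out of the residual. With 100 patients per practice, the practice-mean variance is ICC + (1−ICC)/100, or 0.0199 at ICC 0.01. On 18 df the expected residual at s = 0.15 is 0.0199 + 20 × 0.0126/18 = 0.0339. The standard error is therefore too large by √(0.0339/0.0199) = 1.31.

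Simulated power, with the effect set for about 80% when both factors are in the model:

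| Both never admitted | s = 0.05 | s = 0.10 | s = 0.15 |
|---|---|---|---|
| ICC 0.01 | 78.4% | 71.5% | 60.1% |
| ICC 0.02 | 79.1% | 74.5% | 66.9% |
| ICC 0.05 | 79.8% | 77.7% | 73.8% |

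Repeat runs agree within about one point (59% at the lowest). Type I error at s = 0.15 is 1.3-2.0% for ICC 0.01-0.02. At ICC 0.01 that shift makes up 0.0126/(0.0126 + 0.01) = 56% of between-practice variance, so it is an upper-end assumption.

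**3. If the rule sometimes admits them.** With 60 (low) or 160 (high) patients per practice, varying within group, and ICC 0.01-0.02, power at the three shifts is 78-80%, 72-78% and 61-75% if strong means |r|>0.2. It is 79-81%, 75-79% and 73-79% at |r|>0.1, and not reduced if strong means p<0.05. With both fixed it is 79-81%.

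**4. Dependence on the reading.** Twelve readings were compared: four correlation cut-offs (p<0.05, |r|>0.1, 0.2, 0.3) by three imbalance cut-offs (p<0.05, p<0.10, standardized difference >0.1).
- Covariates with slopes 0.10-0.30 (R² 0.225): about 4 distinct models per trial. The readings disagree on p<0.05 in 11-12% of trials with an effect and about 4% without. Picking the reading by its result gives type I error of 6.9-7.0%, against 5.1-5.4% with covariates fixed.
- Weaker covariates (slopes 0.03-0.15, R² about 0.03-0.04): about 3.7 models, disagreement in 4.4-5.4% with an effect and 1.5-2.1% without. Picking adds 1.0-1.4 points.
- Any single reading fixed in advance, in the first setting: type I error 4.0-5.4%.

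**5. Cost of fixing unrelated factors.** The df fall from 18 to 16 (main effects) or 15 (four cells). Power falls by 0.6-0.9 or 0.9-1.0 points.

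**The case against.** The strongest reply is that the harm is modest. No single reading fixed in advance raises type I error, omission of the randomisation factors errs on the safe side, and the largest power losses need strong shifts, a low ICC and factors that never enter. That stands, and it limits how serious the point is.

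The disagreement between readings also depends on the assumed covariates. The 11-12% figure comes from slopes that straddle the cut-offs tried, and weaker covariates bring it to 4-5%. It should be read as a range.

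The sizes in step 3 probably overstate the loss. With 16 and 8 patients per month and later 2020 starts, a patient-level chi-square would admit both factors in 1.5%, 20% and 38% of allocations (practice-size CV 0.1, 0.2, 0.3), against 0.3-0.5%, 12-13% and 28-29% under the sizes assumed there. More frequent entry means less power lost. The outcome was also simulated as normal, whereas the real one is summed paid claims.

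Three stronger readings are tempting and not supported. A reader might infer that the rule in itself inflates false positives; it does so only if the reading is chosen by its result. A reader might infer that the correlation trigger exposes the treatment contrast; correlation with cost can be examined pooled over arms, although section 6.2 does not promise this. And a reader might take it as stated that the balance tests decide covariate entry; that link is an inference from their place in the section. Nor are different covariates for different outcomes a fault in themselves.

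None of this supplies the missing cut-offs, list or randomisation factors.

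**Conclusion.** The point holds as one that should be corrected, not as a threat to validity. Section 6.2 does not determine the primary model, and it gives no assured place to the two factors that structured the randomisation. That much follows from the text and needs no assumption.

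The consequences are a model that varies with the reading, balance tests that over-flag, and lost precision when volume and year relate to cost. The loss ranges from negligible to about 20 points of power at the far end of the assumptions. These sizes rest on assumed ICC, practice size, factor shifts and covariate strength and show scale only. It would be wrong to conclude that the primary test is anti-conservative as written: omission pushes the other way, and the upward risk of roughly 1-2 points arises only from choosing after results are seen.

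**What to change.** In section 6.2, replace the selection rule with a covariate set fixed before outcome data are examined and entered whatever the balance or correlation:
- Volume group and rollout year, as two main effects or as the four randomisation cells, stated in advance.
- A short list of patient-level baseline variables available in both arms, for example age, gender, race, insurance plan, Charlson index and index-visit PHQ-9 total. Section 6 supports this: "Patient demographics, Charlson comorbidity score, and utilization will be obtained from the electronic medical record and billing systems". The PHQ-9 is part of eligibility in both arms. The exact list is the sponsor's choice; what matters is that it is fixed.
- A statement of whether the set also serves pharmacy cost, the utilization models and the diagnosis strata.
- A statement of whether the matched control and shared go-live month enter the primary model or a sensitivity analysis.

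The social items in section 5.1.2 are recorded at enrollment, and usual care has no follow-up behavioral service (section 5.3). Leave them out unless both arms have them.

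Keep the baseline comparison as a descriptive secondary objective, with standardized differences, that does not select the model. Make adjustment for observed imbalance a named sensitivity analysis. Patients are identified after their practice is randomised (section 4.2: "Patients will begin accruing based on the time the practice goes live"), so some imbalance may be real and not chance.

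The cost is wording plus 2 or 3 of about 18 degrees of freedom, at most about one point of power if the factors are unrelated to cost. No new data or patient contact is needed. The timeline in section 7 places analysis after the wait for claims, which leaves time to settle the list first.
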